3.4 Study Duration

Subjects will be “on study” for up to 53 days depending on the duration of the screening window (up to 45 days) and Group assignment.

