7.2 Visit Description

7.2.1 Visit 1, Screening (Day -44 to Day 0)

All Subjects:

- Preliminary review of inclusion and exclusion criteria
- Obtain signed informed consent for study participation
- Allocation of unique subject number; this number will be used to document the subject data in the case report forms (CRFs) and enrollment log
- Demography – date of birth, gender, race
- Medical/surgical history- all relevant prior medical and surgical conditions will be recorded in the CRF. Documented medical conditions will also note the month and year of onset if the condition is still active.
- Concomitant Medications (within 30 days before injection).
- Vital signs (body temperature, heart rate, blood pressure, and respiratory rate after at least 1 minute in a resting position)
- ECG – The Electrocardiogram (ECG) reading will be assessed for clinical significance by the investigator, and any clinically significant abnormal findings will be noted on the subject’s medical history.
- Clinical laboratory tests – study subjects will have blood obtained for hematology, chemistry, and RA panel (see [Section 8.6.2.4](#)).
- Urine collection for routine urinalysis
- A urine pregnancy test for women of child-bearing potential. Females of child bearing potential are defined as women that are not surgically sterile (hysterectomy or bilateral oophorectomy) nor postmenopausal for at least 1 year prior to screening. Women who are not of childbearing potential will not require a pregnancy test.
- Physical examinations will include an assessment of height, weight and calculation of BMI and an examination of general appearance, skin, eyes, ears, nose, throat, head and neck (including thyroid), lungs, heart, abdomen, lymph nodes, musculoskeletal, and nervous system. Any clinically relevant finding is to be documented as a baseline finding. Physical exams that are conducted as standard of care prior to signing informed consent may be used if they are performed within 30 days of injection.
- RA Evaluation: The swollen and tender joints will be identified and documented during by physical examination as established by the 2010 ACR/EULAR, a DAS28 evaluation and a characterization of the subject’s RA history including previous treatments, date of symptom onset and date of diagnosis.
- Final confirmatory review of inclusion and exclusion criteria

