Changes in health occurring after consent and prior to the day of injection will be added to the subject's medical history unless related to a study procedure.

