8.6 Safety

8.6.1 Adverse Events

8.6.1.1 Definition of Adverse Event

The definitions below follow International Conference on Harmonization (ICH) – Good Clinical Practice (GCP) (see also ICH Guideline for Clinical Safety Data Management: Definitions and Standards for Expedited Reporting).

Adverse Event (AE)

An AE is defined as any untoward medical occurrence in a subject administered a pharmaceutical product and which does not necessarily have a causal relationship with this treatment. An AE can therefore be any unfavorable and unintended sign (including an abnormal laboratory finding), symptom, or disease temporally associated with the use of a medicinal (investigational) product, whether or not considered related to the medicinal (investigational) product.

Any clinically significant change in a condition (worsening) from screening that results in a change in subject management will be considered an AE and will be recorded on the AE page of the CRF.

By definition for this study, all untoward medical occurrences beginning on the day of Visit 2 Baseline (Day 1) through the assessment of Visit 3 Follow-up () are to be reported as AEs. AEs continuing after study completion will be followed to normalization or stabilization. Additionally, untoward medical events occurring prior to the day of Tc 99m tilmanocept administration will be collect and added to the subject's medical history unless they are related to a study procedure in which case the event will be recorded as an AE. SAEs will be reported from the time of consent through the end of participation.

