8.6.2.2 Vital Signs

Vital signs comprise the measurement of body temperature, heart rate, respiration, systolic and diastolic blood pressure. All measurements will be taken after the subject has been in a resting position for at least 1 minute.

Vital signs will be measured at screening, within 15 minutes before investigational product injection, within 15 minutes post injection, and at the follow-up safety visit.

Any clinically significant change from screening (worsening) that results in a change in subject management will be considered an AE and will be recorded on the AE page of the CRF.

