8.6.2.4 Clinical Laboratory Parameters for Screening and Safety

Clinical laboratory tests to be evaluated in this study include hematology, serum chemistry, and urinalysis. Clinical laboratory tests will include the following as defined in Table 2.

Table 2. Clinical Laboratory Parameters

Hematology	Hemoglobin (Hgb), hematocrit (HCT), platelets, neutrophils, basophils, lymphocytes, monocytes, red blood cells (RBC), white blood cells (WBC)
Serum chemistry	Aspartate aminotransferase (AST), alanine aminotransferase (ALT), alkaline phosphatase, total bilirubin, creatinine, chloride, potassium, sodium, total protein, albumin, carbon dioxide (CO ₂)/bicarbonate, blood urea nitrogen (BUN), glucose
Urinalysis	pH, specific gravity
Rheumatoid Panel*	Erythrocyte Sedimentation Rate (ESR), C-Reactive Protein (CRP), Rheumatoid Factor (RF); Anti-Citrullinated Peptide Antibody (ACPA)

* Only at screening; The site laboratory will provide the necessary supplies to collect the blood and urine samples.

All laboratory reports must be promptly reviewed for clinical significance by the investigator, and upon review, initialed and dated by the investigator.

Good clinical practice would suggest that a copy of the laboratory results also be provided to the subject's referring physician.

Any change in a laboratory value, which results in a change in subject management (additional controls or treatment required), will be reported as a clinically significant change. Clinically significant changes in laboratory parameters, which are not the result of laboratory error, are to be recorded as AEs.

Any clinically significant changes in laboratory values are to be followed up with repeated tests at appropriate intervals (as determined by the investigator) until the values return to baseline level or until the abnormality is explained by the investigator.

The expected amount of blood to be withdrawn is shown in Table 3.

Table 3. Approximate Amount of Blood Withdrawn

Time point of examination		Blood Volume
Screening: Laboratory examination	Chemistry 5 mLs Hematology 4 mLs RA Panel 4 mLs	13 mL (~2.6 tsp)
Pre-Injection	PK Sample	5.5 mL (~1.1 tsp)
Post-Injection	PK Samples	26 mL (~5.3 tsp)
Follow-up	Chemistry 5 mLs Hematology 4 mLs	9 mL (~2 tsp)
TOTAL:		54 mL (~11 tsp)

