9.5.4 Analysis of RPK and Dosimetry Variables

The RPK variables for Groups 10 and 11 are the whole blood and urine radioactivity levels per time point. The radioactivity in whole blood will be measured directly using the blood samples. The radioactivity of urine will be obtained from counts of the bladder wall obtained from radiation dosimetry. RPK parameters will be estimated for each subject using noncompartmental models. Summary statistics (n, mean, std, CV, geometric mean) will be computed for each RPK parameter across all subjects by Group (10, 11).

For dosimetry data, for each dosimetry parameter, summary statistics (n, mean, std, and a one standard deviation width confidence interval) will be computed by organ type and overall across all subjects by Group (10, 11). Analysis of Safety Variables

The number and percentage of subjects with any pharmacologic activity or ADRs will be tabulated by dose group and overall.

All adverse events (AEs) will be observed for each subject from the time of signing of informed consent until exit from the study. A treatment emergent adverse event is defined as an adverse event whose start date is on or after the procedure date. If the procedure date and/or the AE start date are missing, the AE will be considered treatment emergent.

Prior to analysis, all adverse events (AEs) will be coded using the MedDRA coding dictionary. Based on these coded terms, treatment emergent AEs will be summarized by dose group and overall as follows:

- by system organ class and preferred terms
- by system organ class and preferred terms and relation to study drug
- by system organ class and preferred terms and severity

Observed and change from baseline vital sign parameters, ECG parameters and hematology, clinical chemistry and urinalysis parameters will be summarized using descriptive statistics (mean, median, standard deviation, minimum, maximum and range) at each time point by dose group and overall.

Other safety analyses will be described in the Statistical Analysis Plan (SAP) for the study.

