Appendix 1 Schedule of Events

Evaluation	Visit 1 Screening	Day 1 Prior to Injection	Visit 2 Baseline: Day 1						Visit 3 Follow-up	
	Days -44 to 0		- 00:15 to -00:01	00:00- 00:05	00:01 to 00:15	15± 5 Mins	60 ± 15 Mins	180 ± 15 Mins	18-20 Hours Post Injection ^b	Day 5 ± 2 ^a
Informed Consent	x									
Entry Criteria	x									
Medical History, RA History and Demography	x									
Urine Drug Screen	x									
ACR/EULAR 2010 Classification	x									
Vital Sign Assessment	x		x		x				x	x
ECG	x		x		x				x	x
Physical Examination	x								x	x
DAS-28	x									
Clinical Laboratory Evaluation: Chemistry, Hematology, UA	x								x	x
Rheumatoid Arthritis Panel	x									
Urine Pregnancy Test	x	x								
Tilmanocept Administration				x						
Whole Body Planar and Optional 3D SPECT or SPECT/CT Image^a							x ^a	x ^a		
Whole Body Planar Image for Dosimetry Evaluation^b						x ^b	x ^b	x ^b	x	
Planar SPECT Imaging of Hands							x	x		
Blood Collection for PK Analysis^b			x ^b	x ^b		x ^b	x ^b	x ^b	x	
Concomitant Medications	x	x							x	x
Adverse Event Monitoring	x	x	x	x	x	x	x	x	x	x

[figure not shown]
^a Groups 1-9 only

^b Groups 10 and 11 only

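### Post-injection worsening is judged against screening values up to 45 days old, and no laboratory sample is taken on Day 1 before injection, so changes already present at dosing can be recorded as treatment-emergent and, for laboratory values, may be counted as ADRs

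*Combined protocol and SAP*

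**What the plan says.** **Reference for worsening.** For vital signs, Section 8.6.2.2 states: "Any clinically significant change from screening (worsening) that results in a change in subject management will be considered an AE". The general rule in Section 8.6.1.1 uses the same reference: "Any clinically significant change in a condition (worsening) from screening that results in a change in subject management" is an AE. Sections 7.2.2.1, 8.6.2.2 and 8.6.2.3 nevertheless schedule vital signs and ECG in the 15 minutes before injection. The ECG section names no reference.

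**Age of the screening value.** Section 3.4 gives time on study as "depending on the duration of the screening window (up to 45 days) and Group assignment".

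**Laboratory schedule.** In Appendix 1 the row "Clinical Laboratory Evaluation: Chemistry, Hematology, UA" is marked at screening and Visit 3 only. The Day 1 pre-injection list in Section 7.2.2.1 contains no safety laboratory test, and the only pre-injection blood in Table 3 is a PK sample. Section 8.6.2.4 adds: "Clinically significant changes in laboratory parameters, which are not the result of laboratory error, are to be recorded as AEs". It treats a change as clinically significant when it alters management, and names no reference time.

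**Analysis.** Section 9.5.4 states: "Observed and change from baseline vital sign parameters, ECG parameters and hematology, clinical chemistry and urinalysis parameters will be summarized using descriptive statistics". It does not say which measurement is the baseline. It calls an AE treatment-emergent if its start date is the procedure date or later, or if either date is missing.

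**Sorting events by time.** Under Section 7.2.1, "Changes in health occurring after consent and prior to the day of injection will be added to the" medical history, unless related to a study procedure. Sections 8.6.1.1 and 8.6.1.3 make anything that begins on Day 1 an AE, whether before or after the injection.

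**Route to the primary endpoint.** Section 5.3 treats an event as an ADR when a causal link is at least reasonably possible, that is, not excluded. Section 8.6.1.2 counts possibly related as related. Section 9.2 requires the ADR to be observed after the dose. In Section 5.3, one event among three subjects expands the cohort, and further events set the MTD.

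**The concern.** The AE rule asks whether a subject is worse than at screening. The safety question is whether the subject is worse than just before injection. The two can differ in both directions. A change that developed before Day 1 looks like worsening after the drug. A subject who had improved since screening can worsen after injection, back to the screening level, without meeting the screening-based rule. For vital signs and ECG the better reference is already collected.

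For laboratory values there is no better reference. Section 7.2.1 can send a change to medical history only if someone has seen it, and a silent laboratory change in the gap is first measured at Visit 3. It is then observed after the dose, as Section 9.2 requires, with no pre-dose value close to injection to help attribute it. Section 1.3.2 reports dose-related AST increases in rats as the tilmanocept-related clinical pathology finding, so this panel is one where attribution matters. At stake are the treatment-emergent AE tables and, through laboratory AEs judged possibly related, the ADR count that drives escalation.

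**Working it through.** **1. The plan's own figures.** Inputs are the Table 4 probabilities for Groups 1-9: .01, .02, .05, .08, .10, .13, .16, .19, .22. I read the Section 5.3 rule as follows.
- 0/3, or 1/3 then 0/3: escalate.
- 1/3 then 1/3: the current dose is the MTD.
- 1/3 then 2 or more, or at least 2 of the first 3: the previous dose is the MTD.

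For event probability p, P(escalate) = (1-p)^3 + 3p(1-p)^2 × (1-p)^3. The expected number in a group is P(reached) × [3 + 3 × 3p(1-p)^2]. Running this through nine groups gives an average of 26.5 subjects (stated 26.3) and P(MTD is Group 7) = 0.153 (stated 0.152). The whole MTD row agrees within 0.001. P(all nine groups cleared) = 0.270. The rule as read is therefore the one behind Table 4.

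**2. Length of the laboratory comparison, Groups 1-9** (screening on Day -44 to 0, injection on Day 1, Visit 3 at 3 to 7 days after injection).
- Longest gap before injection: Day -44 to Day 1 = 45 days. Comparison: 45 + 3 = 48 to 45 + 7 = 52 days. Share after injection: 3/48 = 6% to 7/52 = 13%.
- Shortest: screening on Day 0 and Visit 3 at 3 days, 1 + 3 = 4 days, of which 3 follow injection.

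**3. What a small misattribution rate would do.** Let f be the probability that a subject has a pre-injection change counted as an ADR. The documents give no value, so f is an assumption. Suppose the drug causes no ADRs.
- P(a three-subject cohort expands or stops) = 1 - (1-f)^3.
- P(escalation stops before clearing Group 9) = 1 - [(1-f)^3 + 3f(1-f)^5]^9.

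| f | Cohort expands or stops | P(escalate), one group | Stops before clearing Group 9 |
|---|---|---|---|
| 1% | 0.030 | 0.9988 | 0.010 |
| 2% | 0.059 | 0.9954 | 0.040 |
| 5% | 0.143 | 0.9734 | 0.215 |
| 10% | 0.271 | 0.9061 | 0.588 |

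**4. The same f on top of Table 4**, with p' = 1 - (1-p)(1-f). P(MTD is Group 6 or lower, or none) moves from 0.364 at f = 0 to 0.465 at 2% and 0.614 at 5%. Average sample size moves from 26.5 to 25.3 and 22.9.

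**5. Which route leads where.**
- *Vital signs and ECG.* A reading minutes before injection exists, so the investigator can see that a change predates the dose, and Section 9.2 then argues against an ADR. The change can still be an AE by comparison with screening, and treatment-emergent if dated Day 1.
- *Laboratory values.* No pre-injection reading exists near the dose. A change first found at Visit 3 is observed after the dose, can be rated possibly related, and so can be an ADR. Section 9.5.4 also treats a missing start date as treatment-emergent.

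**The case against.** The plan has real safeguards. Section 8.6.1.2 lets the investigator rate an event probably or definitely not related, on the grounds of clinical state or other therapy. Section 8.6.2.4 requires follow-up of a significant change until it returns to baseline level or is explained. Section 4.1.1 requires stable methotrexate, NSAIDs and corticosteroids for more than 4 weeks, and biologics for more than 8 weeks, before Day 1. Section 4.1.2 excludes renal and hepatic insufficiency. Only changes that alter management count, so ordinary drift is not an AE. Calling Visit 2 Baseline also suggests a Day 1 reading for vital signs and ECG. These points stand. They make misattribution less frequent, but none supplies a laboratory value close to injection.

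Four stronger readings are tempting and are not supported.
- *Every silent laboratory change must become an ADR because it cannot be excluded.* Section 5.3 asks for a reasonable possibility, and the causality scale allows a negative judgement. The missing sample makes attribution harder; it does not decide it.
- *The vital-sign rule feeds escalation as the laboratory gap does.* It governs what is recorded as an AE, and the pre-injection reading and Section 9.2 weaken any route to an ADR.
- *At 2-5% per subject, the chance of at least one case among 27 subjects (1 - 0.98^27 = 42% to 1 - 0.95^27 = 75%) measures the damage.* That is the chance that an assumed event occurs at all, not the chance of a changed decision.
- *The short follow-up of 18-20 hours in Groups 10-11 distorts the MTD.* Those groups are dosed after the MTD is set, so only their safety summaries are affected.

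**Conclusion.** The point holds in two parts. First, screening is the wrong reference for post-injection vital-sign AEs when a reading within 15 minutes before injection exists, and treatment emergence by calendar date cannot separate Day 1 findings before injection from those after it. This affects AE recording and the safety tables; a route from vital signs into the escalation decision is not shown.

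Second, a laboratory change that alters management and arose silently in the screening gap often cannot be separated from a drug effect, and may be counted as an ADR. The effect on escalation is 6-14% per three-subject cohort and 4-22% for stopping early. Both ranges assume a 2-5% misattribution rate and no true ADRs. At 1% the chance of stopping early is 1%. The true rate is unknown and should be smaller when screening falls close to Day 1. The documents do not support saying that the MTD will be wrong, only that the plan gives up an inexpensive means of protecting it.

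**What to change.** 1. **Reference.** In Sections 8.6.1.1 and 8.6.2.2, judge post-injection vital-sign worsening against the Day 1 pre-injection reading, and keep screening as history. In Section 9.5.4, state that baseline for vital signs and ECG is that reading. State also that the laboratory baseline is the screening value unless step 3 is adopted.
2. **Treatment emergence.** In Sections 8.6.1.1, 8.6.1.3 and 9.5.4, define it by onset after the time of injection. Onset time is already required by Section 8.6.1.3. Findings present before injection on Day 1 then go to medical history unless related to a study procedure, and the sentence in Section 7.2.1 should be aligned. An event dated Day 1 with no onset time can stay treatment-emergent, in line with the existing missing-date rule. Without this step, an abnormality found before injection on Day 1 would still be classed as a treatment-emergent AE, even if step 3 were adopted.
3. **Optional laboratory baseline.** Draw the existing chemistry and hematology panel and urinalysis on Day 1 before injection. The Groups 1-9 laboratory comparison then spans 3 to 7 days.

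**Cost.** Steps 1 and 2 are wording, carried in a protocol amendment. Step 3 adds one routine panel and urinalysis per subject at an existing visit, and about 9 mL of blood (5 mL chemistry + 4 mL hematology in Table 3). In Groups 1-9, which give no PK blood, the total rises from 13 + 9 = 22 mL to 31 mL. In Groups 10-11 it rises from 54 to 63 mL. Steps 1 and 2 are worth making even if step 3 is declined, but they leave the laboratory gap open.

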8.6.2.3 Electrocardiogram

A standard 12-lead electrocardiogram (ECG) will be obtained at screening, as well as 15 minutes before investigational product injection, within 15 minutes after investigational product injection, and at the follow-up safety visit. The ECG will be measured with the subject in a resting position for at least 1 minute. No continuous ECG monitoring will be required. At a minimum the heart rate, QRS, PR and QT intervals will be collected. QTc will be calculated using both the Fridericia and Bazett formulas.

On-site investigator's responsibilities

The immediate cardiac safety of the subject will be ensured by the on-site qualified physician. Any 12-lead ECG intervals, waveform abnormalities, and rhythm changes that are clinically significant in that they result in a change in subject management will be considered an AE. In the case of an SAE, once SAE notification is decided upon, investigators are required to follow the procedure described for SAE notification and document abnormal ECG findings (intervals and waveforms). Any interval data or abnormal waveform finding that resulted in an AE (i.e., change of patient management) must be followed to normalization or stabilization.

Each 12-lead ECG tracing must be signed and dated and stored in the subject's source documentation.

8.6.2.4 Clinical Laboratory Parameters for Screening and Safety

Clinical laboratory tests to be evaluated in this study include hematology, serum chemistry, and urinalysis. Clinical laboratory tests will include the following as defined in Table 2.

Table 2. Clinical Laboratory Parameters

Hematology	Hemoglobin (Hgb), hematocrit (HCT), platelets, neutrophils, basophils, lymphocytes, monocytes, red blood cells (RBC), white blood cells (WBC)
Serum chemistry	Aspartate aminotransferase (AST), alanine aminotransferase (ALT), alkaline phosphatase, total bilirubin, creatinine, chloride, potassium, sodium, total protein, albumin, carbon dioxide (CO ₂)/bicarbonate, blood urea nitrogen (BUN), glucose
Urinalysis	pH, specific gravity
Rheumatoid Panel*	Erythrocyte Sedimentation Rate (ESR), C-Reactive Protein (CRP), Rheumatoid Factor (RF); Anti-Citrullinated Peptide Antibody (ACPA)

* Only at screening; The site laboratory will provide the necessary supplies to collect the blood and urine samples.

All laboratory reports must be promptly reviewed for clinical significance by the investigator, and upon review, initialed and dated by the investigator.

Good clinical practice would suggest that a copy of the laboratory results also be provided to the subject's referring physician.

Any change in a laboratory value, which results in a change in subject management (additional controls or treatment required), will be reported as a clinically significant change. Clinically significant changes in laboratory parameters, which are not the result of laboratory error, are to be recorded as AEs.

Any clinically significant changes in laboratory values are to be followed up with repeated tests at appropriate intervals (as determined by the investigator) until the values return to baseline level or until the abnormality is explained by the investigator.

The expected amount of blood to be withdrawn is shown in Table 3.

Table 3. Approximate Amount of Blood Withdrawn

Time point of examination		Blood Volume
Screening: Laboratory examination	Chemistry 5 mLs Hematology 4 mLs RA Panel 4 mLs	13 mL (~2.6 tsp)
Pre-Injection	PK Sample	5.5 mL (~1.1 tsp)
Post-Injection	PK Samples	26 mL (~5.3 tsp)
Follow-up	Chemistry 5 mLs Hematology 4 mLs	9 mL (~2 tsp)
TOTAL:		54 mL (~11 tsp)

